To test the preliminary efficacy of the [REDACTED] Journey of Transformation–Native Youth Health Leadership Program (CHJ) which is an adapted and expanded version of the Discovering Our Story intervention curriculum, a 2010 SAMSHA-identified best practice AIAN strengths-based comprehensive substance use and health risk prevention and health leadership program for AIAN youth.

Outcomes:

- decrease rates of ATOD (marijuana and other drugs) use, intentions to use, susceptibility,
- increase refusal efficacy;
- decrease sexual activity (number of partners, condomless intercourse
- delay sexual initiation,
- increase sexual self-efficacy (i.e., refusal, avoidance), and safer sex intentions.

Examine how stressful life events, mental health (depression/anxiety/self-esteem), cultural protective (identity, enculturation, collectivist values, community connectedness, communal mastery, benevolence/traditionalism) and PYD-related factors (e.g., connectedness, efficacy, ATOD and sexual refusal) moderate or mediate the intervention's efficacy.

1.6 Study design. Provide a one-sentence description of the general study design and/or type of methodology.

Your answer will help HSD in assigning applications to reviewers and in managing workload. Examples: a longitudinal observational study; a double-blind, placebo-controlled randomized study; ethnographic interviews; web scraping from a convenience sample of blogs; medical record review; coordinating center for a multi-site study.

A randomized waitlist stepped wedge design with study participants recruited in staggered cohorts, with those in each annual recruitment wave receiving *individual-level random assignment* to either immediate intervention or waitlist control.

1.7 Intent. Check all the descriptors that apply to your activity. You must place an “X” in at least one box.

This question is essential for ensuring that your application is correctly reviewed. Please read each option carefully.

Descriptor
 1. Class project or other activity whose purpose is to provide an educational experience for the researcher (for example, to learn about the process or methods of doing research).
 2. Part of an institution, organization, or program’s own internal operational monitoring.
 3. Improve the quality of service provided by a specific institution, organization, or program.

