5 PROCEDURES

5.1 Study procedures. Using lay language, provide a complete description of the study procedures, including the sequence, intervention or manipulation (if any), drug dosing information (if any), blood volumes and frequency of draws (if any), use of records, time required, and setting/location. If it is available: Upload a study flow sheet or table to **Zipline**.

For studies comparing standards of care: It is important to accurately identify the research procedures. See UW IRB [POLICY Risks of Harm from Standard Care](#) and the draft guidance from the federal Office of Human Research Protections, ["Guidance on Disclosing Reasonably Foreseeable Risks in Research Evaluating Standards of Care"](#); October 20, 2014.

Information about pediatric blood volume and frequency of draws that would qualify for expedited review can be found in this [reference table](#) on the Seattle Children's IRB website.

Research activities will be conducted by UW and [REDACTED] staff and begin the first week of class: for the waitlist group – the group starting in spring, they will only take the baseline assessment in the Fall and begin the intervention steps as described below beginning in the spring. Thus they receive one more assessment than students in the immediate intervention group (fall). UW staff will be on hand to answer any questions at each assessment time point. Please note the follow-up assessment are about 10 minutes shorter as we will not be any lifetime behaviors questions

Week 1. Take a 30-40 minute online baseline assessment.

UW and [REDACTED] staff will set up laptops or students will have their own laptop. Students will be emailed a link, they will sign onto their laptops and link into the survey. The student

will enter their response directly into the questionnaire. Students will be given a Native designed t-shirt and water bottle.

Weeks 1-3. Meet with a mentor who will help students set goals to improve their health goals around sexual health and/or reduce or avoid alcohol, tobacco, or other substance use. They may meet with the mentor one more time within this time period (for a total of two meetings). The masters-level mentors are provided by the [REDACTED] and trained by a certified motivational interviewer trainer hired by UW.

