Week 1 – 8 (month 1-2). As part of their health class, attend 16 health sessions related to healthy behaviors and developing behavioral skills for health promotion. Sessions will be led by [REDACTED] staff. The study session curriculum will emphasize youth as leaders, storytellers, and environmental stewards and highlight the importance of connecting to their own tribal traditions.

Week 9- 16 (month 3-4). **Optional** additional activity. Participate in once a month activity (booster sessions).

The activities will help build youth leadership skills and include drum making, and storytelling vest making that incorporate their own cultural symbols, and up to two outdoor activity field trips. The field trips are to a places of cultural significance near the school and involve a 30-45 minute hike. Activities are between 1-2 hours and delivered by the [REDACTED] staff after school or on weekends.

Week 9 (Month 3) take the online post intervention assessment via a link sent to their email address by the UW staff

Week 16 (month 4) **Optional** additional activity. Meet with their mentor for a booster MI session to revise their vows for health and community leadership.

Week 9 -24 (month 3 - 6). **Optional** additional activity. Attend a digital storytelling training and up to three monthly planning sessions to prepare for digital storytelling leadership premiere night. Training and planning sessions are 1-2 hours long and held after school. Students will be asked to create a digital story about a health promotion activity of their choice for their community. Some examples may be an increase in cultural activities through participating in traditional games, an increase in promoting healthy lifestyle by planting a traditional garden or a medicine garden base on their own tribal plants. These activities are delivered by the UW and [REDACTED] staff.

Week 24 (Month 6) take the online follow-up assessment via a link sent to their email address by the UW staff

Week 25 (Month 6): **Optional** additional activity. Attend a leadership premiere night, present their digital stories and/or share a story that they have learned about health promotion and celebrate their health leadership journey.

Help prepare the leadership night traditional feast and giveaway that will honor their community culture and values.

Month 12: Take the online follow-up assessment via a link sent to their email address by the UW staff

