These examples are of the most sensitive and risky questions we may ask. None of the measures are intended to capture information on suicidality or some other condition that would need referral or notification to some other entity. Please note the follow-up assessment are about 10 minutes shorter as we will not be collecting any lifetime behaviors questions.

Alcohol, Tobacco and Other Drug Use.

Current alcohol use. Participants will be asked if they drank alcohol in the past 30 days

Problem drinking, GAINS Short Screener for youth

ATOD Age initiation. Age of first alcohol, tobacco, marijuana and other drug use.

Peer Alcohol Associations. Number of friends that drink often, peer encouragement to drink or get drunk.⁴²

Susceptibility to initiate ATOD among self-reported non-smokers, non-drinkers, and non-drug users we will ask 6 questions on a 4-point scale: (eg. "if one of your best friends offered you a cigarette/joint/drink, would you smoke it?").

Specific Event Drug and Alcohol Refusal Efficacy scale (SEDARE) perceived likelihood that youth will use drugs and alcohol in specific situations and inquires whether the respondent would be tempted to use alcohol or marijuana in eight potentially stressful or pressured situations.⁴³

Non-ceremonial tobacco use. Adapted from the NSDUH include current cigarette use, vaping and juuling.

Adolescent Sexual and Reproductive Health.

Sexual activity. Adolescent Sexual Risk Behavior 11-item and Adolescent Sexual Activity Index (ASAI) 10 items assess current and past sexual practices with most items focused on pre-coital behaviors during last 12 months for the sexual activities with other youth. If yes to pre-coital behaviors additional items assess if they have engaged in sexual intercourse, frequency, frequency of sex without birth control, frequency of sex without a condom; number of different sexual partners; and whether or not alcohol or drugs were used at first sex experience and/or last time had sex.

Safer sex intentions. Health Belief Model-Intentions for Safer Sex (HBMI) 7-item/5 pt scale (e.g., "I do not plan on having sex until I am at least 18 years old").

Predictors, Mediators, and Moderators. Spirituality (*Native American Spirituality Scale, Traditional Spiritual Activities scale*)

Standard measures:

Mental health/well-being (e.g., self-esteem, GAD-7, and PHQ-8) for youth and culturally-specific stressors such as familial historical trauma, microaggressions, in-community microaggressions.

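### If scored yes/no, sexual-activity items asked over the last 12 months can barely show a reduction at Week 9; add 30-day versions, and fix non-user status for susceptibility at baseline

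*Protocol*

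**What the plan says.** Protocol section 5.4 (Data variables) describes two sexual-activity scales that "assess current and past sexual practices with most items focused on pre-coital behaviors during last 12 months". A skip rule follows: "If yes to pre-coital behaviors additional items assess if they have engaged in sexual intercourse", together with frequency, condom and birth-control use and number of partners. No window is given for those further items. Follow-up surveys are shorter only because "we will not be collecting any lifetime behaviors questions". Alcohol in the same section has a shorter window: "Participants will be asked if they drank alcohol in the past 30 days".

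Protocol section 1.5 lists, among its outcomes, "decrease sexual activity (number of partners, condomless intercourse", and also delayed sexual initiation.

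The SAP (Statistical Design and Power) makes sexual activity a primary outcome. It tests it by intent to treat through the Intervention by Time term, with a logit link for binary outcomes. It places the test immediately after the intervention, then two months after it, and in the power paragraph three months after it.

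Protocol section 5.1 puts the baseline in Week 1 and the 16 sessions in Weeks 1–8, and then says: "Week 9 (Month 3) take the online post intervention assessment". Of waitlist students it says "they will only take the baseline assessment in the Fall and begin the intervention steps as described below beginning in the spring".

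On susceptibility, another SAP primary outcome, section 5.4 says: "Susceptibility to initiate ATOD among self-reported non-smokers, non-drinkers, and non-drug users we will ask 6 questions". It does not say when non-user status is decided.

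**The concern.** A test of change rests on answers that can change. When two surveys are a few weeks apart and each asks about the previous year, most of the second window repeats the first. A student who was active before baseline and then stops must still truthfully answer yes. On yes/no items the test would then depend almost wholly on new starters. A null result could not separate an ineffective curriculum from an insensitive question.

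The susceptibility items raise a separate and smaller problem. If non-user status is taken afresh at each survey, students who start using leave the measure after randomisation, and the curriculum may affect who leaves. If status is fixed at baseline, the comparison is sound but uses fewer students than the SAP's analysed number.

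**Working it through.** **Sample size used.** The SAP recruits 255 and expects 15% attrition: 255 × 0.85 = 216.75, which agrees with its 216. Equal allocation (assumed) gives 108 per arm. The SAP's power claim is not relied on here. With f = d/2 and r = 0.25, the usual repeated-measures interaction formula gives 73.8% power at 255 for d = 0.20, so it does not return the SAP's figure. That is a separate matter.

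**Share of the second 12-month window that precedes baseline**, (52 − gap)/52:

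| Primary survey | Gap from baseline | Share before baseline |
|---|---|---|
| Week 9 | 8 weeks | 44/52 = 84.6% |
| 2 months after Week 8 | 8 + 8.7 = 16.7 weeks | 35.3/52 = 67.9% |
| 3 months after Week 8 | 8 + 13 = 21 weeks | 31/52 = 59.6% |

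No event rates are needed for this. A 9-week gap gives 43/52 = 82.7%.

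**One worked case (rates assumed).** Suppose 60% of students are active, weekly rates among them are exponential with mean m = 0.25, and the curriculum cuts the rate by 40% from baseline. The chance of at least one event in t weeks is mt/(1 + mt).

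- 12-month item at Week 9, control: 0.25 × 52 = 13, so 13/14 = 92.9%. Treated: 44 + 0.6 × 8 = 48.8 effective weeks, so 12.2/13.2 = 92.4%. The difference is 0.43 points among active students, or 0.26 points overall.
- 30-day item (4.29 weeks), control: 1.071/2.071 = 51.7%. Treated: 0.643/1.643 = 39.1%. The difference is 12.6 points among active students, or 7.6 points overall.

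**Range of cases (all rates assumed).** 20–60% active; weekly mean 0.1–0.5; onset among the rest 0–15% per nine weeks; rate and onset both cut by 40%; 108 per arm; two-sided 5%; linear model adjusted for the baseline answer. Power = Φ(δ/SE − 1.96) + Φ(−δ/SE − 1.96).

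- Week 9, one yes/no item: about 5–22% with 12-month recall against 11–40% with 30-day recall.
- Students per arm whose answer changes by Week 9 (40–60% active): 0.4–11.4 of 108 against 11–26.
- Accurately reported counts, Week 9 (40–60% active): 24–94% against 22–86%. The shared weeks cancel, so 12-month recall costs nothing.
- 21 weeks, 20% active, mean 0.1, 15% onset: 40% with 12-month recall against 33% with 30-day recall. Here the longer window is better.

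**Check with a different event model.** Baseline 12-month prevalence was set at 20%, 40% or 60%, with complete cessation in the treated arm and an 8-week gap. The 12-month item then shows arm differences of only 1.9–6.1 points and power of 14–35%. The 30-day item has 13–99%. It gains most where behaviour is common and clustered (99% against 14%), is about equal at 20% prevalence, and is slightly lower at 40% with a uniform rate (24% against 28%).

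**Susceptibility.** If 40–80% of students are non-users at baseline (assumed), the analysed number is 216 × 0.4 = 86 to 216 × 0.8 = 173. Scaling the SAP's d = 0.20 by √(216/n) gives 0.20 × 1.58 = 0.32 down to 0.20 × 1.12 = 0.22.

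**The case against.** The strongest reply is that the plan never says these items are scored yes/no. A skip rule can follow a frequency question just as well, one of the instruments is an index, and the SAP plans one model per outcome, not item by item. No index score was simulated. This stands: the loss shown applies to yes/no scoring, and accurate counts do not suffer it.

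Second, the outcomes named in section 1.5 are chiefly partners, condomless intercourse and initiation. The first two have no stated window. Initiation in 13–16-year-olds is an onset, which a 12-month item does register. This also stands, and it is why the 12-month items should be kept.

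Third, the 30-day form is not always better. It can lose at later time points, or when behaviour is rare and onset drives the effect. At Week 9 it also looks back to about Week 5, before all sessions have been delivered. That limits the recommendation but does not remove it.

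A reader might infer that 12-month items cannot change at all, that the trial cannot detect any effect on sexual activity, or that 30-day recall would give adequate power. The documents support none of these. Onset moves the answer, scoring is unstated, several component items have no stated window, and with a 40% cut no 30-day yes/no case examined reached 80%.

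On susceptibility, a reader might infer serious bias. Nothing in the documents shows it. The fault is an unstated rule, and the effect is probably small.

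**Conclusion.** The point holds in a limited form. The overlap is plain arithmetic: about 85% of the window at Week 9, and 68% or 60% if the SAP's two- or three-month labels mean time after Week 8. If the items are scored yes/no, reductions among already active students are largely hidden at Week 9. Power per item is then about 5–22%, against 11–40% with 30-day recall. Those power figures rest on assumed prevalence, event rates, onset and effect, none of which the documents give.

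The Week 9 comparison also assumes that both arms are surveyed then. Section 5.1 describes no waitlist survey between the fall baseline and spring. This and the three SAP labels for the primary time point must be reconciled before any recall window can be judged properly.

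For susceptibility, the gap is the missing statement of when non-user status is set, and the analysed number will be below 216. Taken together, this is a cheap improvement and not a defect that invalidates the trial.

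**What to change.** - Keep the 12-month items. Add past-30-day versions, the window already used for alcohol, at baseline and every follow-up.
- If Week 9 is the primary time point, use the 30-day version of any yes/no pre-coital items in the SAP model. Otherwise keep 12-month recall for onset and counts, and report both.
- State response format, scoring, and the window for the intercourse, condom and partner items.
- Settle one primary time point across the SAP and section 5.1, and survey both arms in the same calendar week.
- State that non-user status for susceptibility is set at baseline. Ask and analyse all baseline non-users by randomised arm whatever their later use, and give the expected analysed number.

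The cost is a few REDCap items, a small IRB modification and some SAP wording. The downsides are a slightly longer survey, lower prevalence per item, departure from the scale's 12-month form, and a 30-day window at Week 9 that falls within curriculum delivery. Section 7.2 has students arriving two weeks before classes, so a Week 1 30-day baseline would also mix home and dormitory time. That is equal in both arms but may weaken the correlation with follow-up.

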5.8 Genomic data sharing. Will the research obtain or generate genomic data?

X	No
	Yes

→ If yes, answer the question below.

a. Will genomic data from this research be sent to a national database (for example, NIH’s dbGaP database)?

	No
	Yes

→ If yes, complete the [SUPPLEMENT Genomic Data Sharing](#) and upload it to [Zipline](#).

5.9 Whole genome sequencing. For research involving biospecimens: Will the research include whole genome sequencing?

Whole genome sequencing is sequencing of a human germline or somatic specimen with the intent to generate the genome or exome sequence of that specimen.

X	No
	Yes

5.10 Possible secondary use or sharing of information, specimens, or subject contact information. Is it likely that the obtained or collected information, specimens, or subject contact information will be used for any of the following:

- Future research not described in this application (in other words, secondary research)
- Submission to a repository, registry, or database managed by the study team, colleagues, or others for research purposes
- Sharing with others for their own research

Please consider the broadest possible future plans and whether consent will be obtained now from the subjects for future sharing or research uses (which it may not be possible to describe in detail at this time). Answer **YES** even if future sharing or uses will use de-identified information or specimens. Answer **NO** if sharing is unlikely or if the only sharing will be through the NIH Genomic Data Sharing described in question 5.8.

Many federal grants and contracts now require data or specimen sharing as a condition of funding, and many journals require data sharing as a condition of publication. "Sharing" may include (for example): informal arrangements to share banked data/specimens with other investigators; establishing a repository that will formally share with other researchers through written agreements; or sending data/specimens to a third party repository/archive/entity such as the Social Science Open Access Repository (SSOAR), or the UCLA Ethnomusicology Archive.

 No
 Yes

→ If yes, answer all of the questions below.

a. Describe what will be stored for future use, including whether any direct or indirect (e.g., subject codes) identifiers will be stored.

De-identified assessment data will be stored.

b. Describe what will be shared with other researchers or with a repository/database/registry, including whether direct identifiers will be shared and (for specimens) what data will be released with the specimens.

De-identified assessment data.

c. Who will oversee and/or manage the sharing?

Indigenous Wellness Research Institute Director of Research and the PI

d. Describe the possible future uses, including limitations or restrictions (if any) on future uses or users. As stated above, consider the broadest possible uses.

Examples: data will be used only for cardiovascular research; data will not be used for research on population origins.

The study de-identified data will be available after publication of the main study manuscripts; other resources such as training manuals and curriculum will be available after demonstration of their efficacy. All requests from other researchers will be considered on a case-by-case basis by the study investigators and research partners. Researchers requesting access will have to submit a request in writing describing their qualifications including their certification by their local IRB, analytic plans and other uses of the data/resources, and plans to secure the confidentiality and safety of the data. They will be required to agree in writing that they will not share the data with others, will use it only for the research purpose(s) they delineated, and will return or destroy the data upon completion. In order to maintain protection of our participants' privacy, no directly identifying information will be shared with outside investigators. Given the sensitive nature of the data we are collecting including substance use and sexual

behavior among youth, we will not be creating a public access file.

If the UW study team or collaborators from this study use data for future analyses, a data set will be prepared in such a way that the data cannot be relinked to the direct identifiers and the study team could not identify any individuals from the combination of indirect identifiers (age, gender, etc.) in the data set.

For data shared according to NIH requirements, the data set will be prepared in such a way that any indirect identifiers shared are, in our opinion, unlikely to be able to be used to reidentify any individuals.

e. Consent. Will consent be obtained now from subjects for the secondary use, banking and/or future sharing?

	No
	Yes

→ If yes, be sure to include the information about this consent process in the consent form (if there is one) and in the answers to the consent questions in [Section 8](#).

f. Withdrawal. Will subjects be able to withdraw their data/specimens from secondary use, banking or sharing?

	No
	Yes

→ If yes, describe how, and whether there are any limitations on withdrawal.

Example: data can be withdrawn from the repository but cannot be retrieved after they are released.

At any time before the end of the study, a participant may notify UW or [REDACTED] study staff in writing that they would like their data removed from the secondary analysis file and we will honor that request.

g. Agreements for sharing or release. Confirm by checking the box that the sharing or release will comply with UW (and, if applicable, UW Medicine) policies that require a formal agreement with the recipient for release of data or specimens to individuals or entities other than federal databases.

Data Use Agreements or Gatekeeping forms are used for data; Material Transfer Agreements are used for specimens (or specimens plus data). Do not attach any template agreement forms; the IRB neither reviews nor approves them

	Confirmed
-------------------------------------	-----------

5.11 Communication with subjects during the study. Describe the types of communication (if any) the research team will have with already-enrolled subjects during the study. Provide a description instead of the actual materials themselves.

Examples: email, texts, phone, or letter reminders about appointments or about returning study materials such as a questionnaire; requests to confirm contact information.

Study staff will use email, texts, phone, and letters to remind participants about events, trainings, surveys/questionnaire as well as periodic requests to confirm contact information. We will also post information and updates on our study website and member only Facebook page.

5.12 Future contact with subjects. Is there a plan to retain any contact information for subjects so that they can be contacted in the future?

No
 Yes

→ If yes, describe the purpose of the future contact, and whether use of the contact information will be limited to the study team; if not, describe who else could be provided with the contact information. Describe the criteria for approving requests for the information.

Examples: inform subjects about other studies; ask subjects for additional information or medical record access that is not currently part of the study proposed in this application; obtain another sample.

5.13 Alternatives to participation. Are there any alternative procedures or treatments that might be advantageous to the subjects?

If there are no alternative procedures or treatments, select "No". Examples of advantageous alternatives: earning extra class credit in some time-equivalent way other than research participation; obtaining supportive care or a standard clinical treatment from a health care provider instead of participating in research with an experimental drug.

No
 Yes

→ If yes, describe the alternatives.

Any student not interested in the study will have the option to stay in the class, but will not be asked to complete surveys.

5.14 Upload to Zipline all data collection forms (if any) that will be directly used by or with the subjects, and any scripts/talking points that will be used to collect the data. Do not include data collection forms that will be used to abstract data from other sources (such as medical or academic records), or video recordings.

- **Examples:** survey, questionnaires, subject logs or diaries, focus group questions.
- **NOTE:** Sometimes the IRB can approve the general content of surveys and other data collection instruments rather than the specific form itself. This prevents the need to submit a modification request for future minor changes that do not add new topics or increase the sensitivity of the questions. To request this general approval, use the text box below to identify the questionnaires/surveys/ etc. for which you are seeking this more general approval. Then briefly describe the scope of the topics that will be covered and the most personal and sensitive questions. The HSD staff person who screens this application will let you know whether this is sufficient or whether you will need to provide more information.
- **For materials that cannot be uploaded:** upload screenshots or written descriptions that are sufficient to enable the IRB to understand the types of data that will be collected and the nature of the experience for the participant. You may also provide URLs (website addresses) or written descriptions below. Examples of materials that usually cannot be uploaded: mobile apps; computer-administered test; licensed and restricted standardized tests.
- **For data that will be gathered in an evolving way:** This refers to data collection/questions that are not pre-determined but rather are shaped during interactions with participants in response to observations and responses made during those

interactions. If this applies to the proposed research, provide a description of the process by which the data collection/questions will be established during the interactions with subjects, how the data collection/questions will be documented, the topics likely to be addressed, the most sensitive type of information likely to be gathered, and the limitations (if any) on topics that will be raised or pursued.

Use this text box (if desired) to provide:

- Short written descriptions of materials that cannot be uploaded, such as URLs
- A description of the process that will be used for data that will be gathered in an evolving way.
- The general content of questionnaires, surveys and similar instruments for which general approval is being sought. (See the **NOTE** bullet point in the instructions above.)

We will develop in REDCap an online survey data collection tool. Measures will consist of items noted in 5.4 above.

